5. *Comparison intervention practitioner expertise.* Pragmatic trials do not standardize which and how practitioners implement the intervention. In this case, we will cluster-randomize all of the PCPs in our practice to the intervention and will not standardize who or how they will implement the communication strategies. Score = 5.
6. *Follow-up intensity.* Purely pragmatic trials do not have any formal follow-up visits of the individuals and use passive administrative databases to detect outcomes. Given the importance of patient-reported outcomes in this study, we will use a combination of passive and active follow-up methods to ascertain outcomes; these have low respondent burden and only require the completion of short questionnaires. Score = 4.
7. *Primary trial outcome.* Pragmatic trials select outcomes that are meaningful to study participants. Our main outcome will be pain interference, or how pain interferes with a patient's daily life, an outcome identified as meaningful by our patient partners. This outcome is important because while we seek to prevent inappropriate overuse of opioids, the flip side – discontinuing appropriate use of opioids – should also be prevented. The net outcome – pain interference – reflects a balance between inappropriate overuse and underuse of effective pain treatments. Score = 5.
8. *Participant compliance with "prescribed" intervention.* Pragmatic trials measure little or no patient "compliance" with the intervention. When we administer the questionnaires, we will ask whether individuals have received and read the PEAT materials via REDCap but we will not measure adherence to or use of PEATs. Score = 4.
9. *Practitioner adherence to study protocol.* Trials with pragmatic designs use unobtrusive or no methods to measure practitioner adherence to the study protocol. We will measure when and for whom the CDS alerts are activated, but will not report feedback to providers. Score = 4.
10. *Analysis of primary outcome.* PRECIS notes that pragmatic trials include all enrolled patients in the final analysis and there is no separation of the intention-to-treat (ITT) vs. per protocol (PP) patients. We will conduct both ITT and PP analyses for sensitivity analysis purposes. We will ask patients whether they received and read the PEAT materials and will examine when the CDS alerts were fired and for which patients to conduct a PP analysis. Score = 3.

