E4.b. Unit of Randomization. We will randomize the study on the provider level. We will use a random number generator to assign offices to study arms, and will employ multi-level hierarchical models to adjust for clustering within the physician level, described in more detail below.

E4.c. Study Design Overview.

We will auto-enroll all eligible patients to participate in the pragmatic trial and will administer baseline questionnaires as further detailed in the Recruitment Procedures and Outcome Measurement sections below. Patients within the physicians randomized to the CDS arm will not receive the PEAT materials; their physicians will receive the Choosing Wisely alerts via the EHR (Epic Systems, Verona, Wisc.) when appropriate. Patients within the physicians randomized to PEAT will receive the engagement materials via REDCap two days prior to their PCP office visit, supplemented by duplicate paper copies sent via express delivery. For both study arms, patients will receive Clinician and Group Consumer Assessment of Healthcare Providers and Systems (CG-CAHPS) one day after their office visit. They will receive the PROMIS questionnaires every month throughout the study period. We will track follow-up visits through the EHR reports. In all instances, patients may refuse to participate by either not using the PEATs sent via REDCap, or not completing outcome questionnaires.

3. Analysis, Dissemination, and Implementation. In Year 3, we will conduct the statistical analyses and will collaborate with our patient partners to determine the implications of the study results. We present our Dissemination and Implementation plan in full detail below.

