E4.d. Recruitment Procedures (PC-2). Patients meeting inclusion criteria who are managed by one of the 80 participating PCPs at the Cedars-Sinai Medical Network will be auto-enrolled in the study. Patients will receive a written notification via mail of their inclusion in the study and at that time they will be told about the study details, including research procedures and requirements for follow-up, as well as the risks and benefits of study participation. At this time, patients will have the opportunity to actively opt out of receiving the education materials (if they are randomized to PEAT arm). Patients who do not opt out will receive education materials and their care will proceed as usual. Patients who are passively enrolled will receive the study questionnaires via REDCap. We estimate that out of the 4,000 patients eligible for the study (calculated from a quality improvement project based on claims data), approximately 30% will complete all of the questionnaires, which is in line with our sample size calculations. Once the patients complete monthly questionnaires, we will provide a \$5 gift card for filling out the enrollment survey. We have budgeted \$25 per patient as

a financial incentive for completing the questionnaires (Appendix I, **Table 1 for Recruitment Plan** and **Table 2 for Passive Enrollment Estimates**).

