E4.e. Data Collection (RQ-2). Upon auto-enrollment, we will extract the following variables from the electronic health record: chronic pain condition, length of time with chronic pain diagnosis, race and ethnicity, language, marital status, history of pharmacologic treatment, surgical history related to chronic pain condition, past injuries related to chronic pain condition, and length of time with current primary care provider¹³⁷. When the intervention period is initiated, all eligible patients who have any follow-up visits during this 12-month period in both study arms will be sent the questionnaires. We will also capture depression scores via the Patient Health Questionnaires -PHQ-2 and/or PHQ-9 in the EHR. Furthermore, to determine if conversations about opioid medications took place during the visit that was

informed by either the CDS or the PEATS, we will conduct a structured review of a random sample of charts from both study arms.

E5. Statistical Analysis

E5.a. Descriptive and Exploratory Analyses. We will use frequencies and means for univariate descriptive analyses. We will use chi-square tests and paired t-tests to determine whether there are differences between the two study arms; using these bivariate analyses, we will identify covariates and patient- and physician-level moderators to use in the regression models. We will also consult with our Patient Partner to ensure that all appropriate patient-level covariates are included in the final models.

E5.b. Multi-Variate Regression Models. To evaluate the effectiveness of the comparators on the selected outcomes, we will use hierarchical linear regression models to measure changes in the outcomes over time using growth modeling statistical techniques¹³⁸ and will adjust for clustering at the patient, provider, and provider office level. Growth modeling allows the testing of individual differences in outcomes over time. In this study, we will examine HRQOL and communication scores over 12 months for the two study arms. We will adjust for patient- and provider-level covariates to account for potential confounders and also to identify whether there is heterogeneity of the treatment effect (see below). The proposed models are outlined here. We will test both fixed effects and random effects.¹³⁹ (IR-3):

Primary Outcome: Model 1: Hierarchical Linear Model (Longitudinal Analysis)

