Question: Which communication strategy used during the clinical encounter is more effective in reducing pain interference over time for patients with chronic pain who were taking opioids at baseline?

Dependent variable: Pain interference as measured by PROMIS Pain Interference Score (T-Score, Continuous)

Independent variable: Comparator received, CDS vs. PEAT (Dichotomous)

Potential Covariates: Age, gender, race, ethnicity, mental health comorbidities, chronic pain diagnosis, use of other pain medications (neuropathic pain medications, NSAIDS, antidepressants), benzodiazepine use, number of office visits during intervention period, baseline HRQOL, encounter month, physician years of practice, physician gender, employment, SES.

Moderator Analyses: We will use statistical interactions examining the moderating effects of patient age, race, ethnicity, mental health comorbidities, chronic pain diagnosis, physician years of practice and physician gender on the relationship between comparator and pain interference.

Mediation Analyses: We will test whether confidence in decision and satisfaction with communication as measured by COMRADE Scores mediates the relationship between the comparator used and the pain interference outcomes.

Primary Outcome: Model 2: Hierarchical Linear Model (Longitudinal Analysis)

Question: Which communication strategy used during the clinical encounter is more effective in improving how satisfied patients feel over time after communicating with their physician about chronic pain treatment risks and benefits?

Dependent variable: CG-CAHPS

Independent variable: Comparator received, CDS vs. PEAT (Dichotomous)

Potential Covariates: Age, gender, race, ethnicity, educational level, mental health comorbidities, chronic pain diagnosis, use of other prescribed pain medications (neuropathic pain medications, NSAIDS, antidepressants) benzodiazepine use, number of office visits during intervention period, baseline HRQOL, encounter month, physician years of practice, physician gender, employment, SES.

Subgroup Analyses: We will use statistical interactions examining the moderating effects of patient age, race, ethnicity, education level, mental health comorbidities, chronic pain diagnosis; and physician years of practice and gender on the relationship between comparator and pain interference.

Secondary Outcome: Model 3: Hierarchical Linear Model

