Question: Which communication strategy used during the clinical encounter is more effective in improving patient's Health Related Quality of Life over time?

Dependent variable: PROMIS Physical Function, PROMIS Depression, and PROMIS Pain Interference Scores (T-Scored, Continuous)

Independent variable: Comparator received, CDS vs. PEAT (Dichotomous). **Potential Covariates:** Same as Model 2.

Secondary Outcome: Model 4: Hierarchical Generalized Linear Model

Question: Which communication strategy used during the clinical encounter is more effective in reducing opioid prescriptions of more than 90 Morphine Milligram Equivalents (MME) over time?

Dependent variable: Opioid Prescription over 90MME (Dichotomous)

Independent variable: Comparator received, CDS vs. PEAT (Dichotomous). **Potential Covariates:** Same as Model 2.

Other Analyses: We will also perform a differences-in-differences analysis at the beginning and the end of the intervention to determine which strategy resulted in greater reduction in high-risk prescriptions.

Secondary Outcome: Model 5: Hierarchical Generalized Linear Model

Question: Which communication strategy used during the clinical encounter is more effective in reducing co-prescriptions of opioids and benzodiazepines over time?

Dependent variable: Opioids and Benzodiazepines Co-Prescribed (Dichotomous)

Independent variable: Comparator received, CDS vs. PEAT (Dichotomous). **Potential Covariates:** Same as Model 2.

Other Analyses: We will also perform a differences-in-differences analysis at the beginning and the end of the intervention to determine which strategy resulted in greater reduction in high-risk prescriptions.

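### Models 1-5 define exposure as the comparator received, and the plan never makes comparison by randomised arm the primary analysis

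*Combined protocol and SAP*

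**What the plan says.** **Exposure.** In E5.b, Models 1 and 2 (the primary outcomes) list "Independent variable: Comparator received, CDS vs. PEAT (Dichotomous". Models 3-5 repeat it: "Independent variable: Comparator received, CDS vs. PEAT (Dichotomous). Potential Covariates: Same as Model 2".

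**Analysis set.** ITT is mentioned once, in item 10 of the PRECIS list: "We will conduct both ITT and PP analyses for sensitivity analysis purposes". The same item says how the PP analysis is built: "We will ask patients whether they received and read the PEAT materials and will examine when the CDS alerts were fired". Item 8 adds: "we will ask whether individuals have received and read the PEAT materials via REDCap but we will not measure adherence to or use of PEATs".

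**Opt-out.** E4.d says that "patients will have the opportunity to actively opt out of receiving the education materials (if they are randomized to PEAT arm". No matching opt-out is given for the CDS arm. E4.c lets patients in either arm leave questionnaires unanswered.

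**Text that points to assignment.** E4.b says "We will randomize the study on the provider level". E4.c describes patients by the arm to which their physicians were randomised. The paragraph introducing the models says "we will examine HRQOL and communication scores over 12 months for the two study arms". E5.c states power for a difference between arms.

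**Removal of patients.** D2 excludes, after the fact, patients who do not see their PCP in the study period. E7 Missing Data (c) drops those patients and also those lost to follow-up.

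**The concern.** Randomisation protects a comparison of groups as assigned. If the main models group patients by what they received, the comparison also reflects who accepts, opens or triggers the tool.

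The plan gives reason to expect that this matters. Declining the materials is offered in one arm only. E7 Missing Data (a) recognises that not completing surveys, not using the educational tools and poorer HRQOL may go together; a noun is missing from that sentence, but its sense is clear. If non-users of PEAT do worse and leave the PEAT group, PEAT looks better than it is, and the CDS arm has no equivalent step to offset this.

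The primary contrast is also left for the analyst to define, possibly after the data are seen.

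**Working it through.** **1. The passages side by side.** Two readings are possible, and each leaves something unexplained.

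- *Received means actually received.* This fits the literal wording, the model questions (which ask about the strategy used in the encounter) and the separate listing of ITT as a sensitivity analysis. But the PP analysis, built from the same receipt data, would then add little.
- *Received means assigned.* This fits E4.b, E4.c, the introduction to E5.b and E5.c. But Models 1-5 would then already be ITT, and listing ITT as a sensitivity analysis would be redundant.

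Nothing in the plan settles which applies.

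**2. What the two-level variable does under the literal reading.**

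| Patient | Assigned | Received |
|---|---|---|
| PEAT, reports receipt | PEAT | PEAT |
| PEAT, opted out or reports non-receipt | PEAT | neither |
| PEAT, did not answer the receipt question | PEAT | unknown |
| CDS, alert fired | CDS | CDS |
| CDS, no triggering order or risk factor | CDS | neither, if an alert is needed to count |

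Receipt of PEAT is known only from questionnaires, and E4.d expects about 30% of 4,000 patients (1,200) to complete all of them. Models 4 and 5 use prescribing outcomes that need no questionnaire, so exposure could be unknown for patients whose outcome is known.

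**3. The plan's sample size, used below.** For 0.3 SD, 90% power and α 0.05 (two-sided assumed), n = 2 × (1.960 + 1.282)² / 0.3² = 234 per arm before clustering. With ICC 0.02 the multiplier is 1 + (m − 1) × 0.02. The cluster size m is not stated. With m = 19, 234 × 1.36 gives 319, close to the stated 320. With m = 640/80 = 8, 234 × 1.14 gives 267. So 320 can be approached only by solving for m; this does not decide the present point.

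**4. Possible bias if non-receivers fall out (assumed rates, no true effect).** Let a fraction f of the PEAT arm be non-receivers who score g SD worse than receivers. If the whole arm has mean 0, then (1 − f) × R + f × (R + g) = 0, so the receivers' mean is R = −f × g. Excluding non-receivers shifts the contrast by f × g in favour of PEAT.

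The rejection rate uses SE = √[1.14 × (1/320 + 1/(320 × (1 − f)))], with m = 8. For f = 10% the SE is 0.087; for f = 20% it is 0.090.

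| f | g (SD) | Shift f × g (SD) | Share of 0.3 SD | Type I error (nominal 5%) |
|---|---|---|---|---|
| 5% | 0.2 | 0.01 | 3% | 5.2% |
| 10% | 0.3 | 0.03 | 10% | 6.4% |
| 20% | 0.5 | 0.10 | 33% | 20.1% |

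These are raw shifts before any baseline adjustment. Loss of CDS patients without an alert is not included, and its direction is unknown.

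**5. What the assigned-arm analysis does to power.** If 0.3 SD is the assigned-arm difference, the sample size does not change. If it is the effect among recipients and a fraction f of the PEAT arm gains nothing, the assigned-arm difference is 0.3 × (1 − f). At 320 per arm, with the implied design effect 320/234 = 1.37:

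- f = 10%: 0.27 SD, power 83.2%
- f = 20%: 0.24 SD, power 73.8%

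With 480 per arm analysed and m = 960/80 = 12, power is 96.6% and 92.0%.

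**The case against.** The strongest reply is that 'received' is loose wording for the arm's strategy. The design and analysis text repeatedly speaks of arms, receipt data are assigned to the PP analysis, adherence to PEAT is expressly not measured, and a two-level variable has no place for a patient who received neither. Item 10 can also be read as saying only that ITT and PP will be compared. All of this is fair, and it is why the point is that the plan permits an as-treated analysis, not that it prescribes one. It does not remove the gap, since no sentence names the primary analysis set.

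A reader might infer something stronger: that patients are moved into the other arm, or that the randomised comparison is already lost. The documents do not support this. No rule recodes anyone, and a PEAT opt-out has not thereby received CDS. Changes of PCP and visits booked at short notice are not discussed in the plan, so they cannot be counted as departures it builds in. The opt-out covers the materials only; nothing says it ends questionnaires or record follow-up. An alert that fires only when triggered is also how the CDS strategy is meant to work, so a CDS patient without an alert is only a possible loss.

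On size, the objection largely stands. The rates and prognostic differences in the illustration are assumptions. Model 1 is a growth model with baseline HRQOL among its potential covariates, so a stable difference in level may be partly absorbed. A difference in trajectory would not be. At 5% and 0.2 SD the effect is negligible.

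**Conclusion.** The point holds as a gap in the definition of the primary contrast. Read literally, all five models compare patients by receipt, and ITT has no status beyond a sensitivity analysis. Whether this would bias the result, and by how much, cannot be determined from the documents, which give no opt-out rate, non-receipt rate or prognostic difference. Under the values assumed above the shift runs from 0.01 to 0.10 SD before baseline adjustment, against a target of 0.3 SD. Because the plan's opt-out is one-sided and the plan itself anticipates poorer HRQOL among non-users, balance between arms cannot be presumed. The correction is cheap and should be made before outcome data are analysed.

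**What to change.** - **E5.b, Models 1-5:** replace the exposure with the comparator assigned, meaning the randomised arm of the patient's PCP (or office, if that is the unit) at patient enrolment. Hold it fixed regardless of opt-out, receipt or alert firing. Enrolment is the right reference point because Milestone B9 puts randomisation at 7/30/2017, while Milestone E2 has enrolment ending on 12/31/2018.
- **PRECIS item 10:** state that the assigned-arm (ITT) analysis is primary and PP is the sensitivity analysis.
- **E4.b and Milestone B9:** reconcile the unit. E4.b says providers are randomised but then assigns offices, and B9 refers to network offices.
- **D2 and E7 Missing Data (c):** reconcile the rules that drop patients with the ITT label. At minimum, keep patients lost to follow-up in the likelihood-based model with the data they have, and justify or revise the exclusion of patients with no PCP visit.

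The cost is wording plus a record of each patient's PCP or office and its arm at enrolment. No new sample size is needed if 0.3 SD is the assigned-arm difference. The downside is that the assigned-arm effect may be smaller than the effect among recipients, with the power loss shown above if 0.3 SD was meant for recipients. The PP analysis would still report the recipient comparison.

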E5.c. Power Calculations. Guided by previous work in chronic pain interventions,¹⁴⁰ we calculated sample size using an intracluster correlation coefficient of 0.02, an α level of 0.05, 90% power, and detection of a mean (SD) difference of 0.3 standard deviations on the PROMIS Pain Interference scale. We calculated a sample size of 320 patients per study arm, for a total of 640 patients. To compensate for predicted loss to follow-up, multiple variables in the final multi-level models, as well as sub-group analyses, we inflated the sample size by 50% to 960. Since we will be examining the effect of the interventions on a variety of sub-groups within the study sample, such as diagnoses of mental health conditions, race, ethnicity, gender, and chronic pain diagnosis, we will be adequately powered to detect meaningful differences. In our original proposal, we calculated a sample size of 320 patients per study arm for a total of 640 patients. To compensate for predicted loss to follow-up and non-response we had inflated the recruitment target size by 50% to 960. Under the current modification – and given the absence of changes to the assessment schedule, the estimated intracluster correlation coefficient, and the expected mean difference - the sample size required to adequately power the analysis remains unchanged. We believe the recruitment target will also remain consistent, and potentially even fall due to the ability of study staff to call passively enrolled patients and remind them to respond to assessments. We therefore anticipate being adequately powered to detect meaningful differences between the two arms.

E6 Heterogeneity of Treatment Effect (HT-1, HT-3, HT-4)

After reviewing the literature and consulting with our patient partners, we identified specific subgroups we plan to analyze to identify whether there is a heterogeneity of the treatment effects. Below we detail our planned sub-group analyses, our hypotheses, and our plans for statistical analysis for each subgroup. In order to address the problem of multiplicity, a Bonferroni correction will apply to all analyses.

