Attachment C-R: Milestone Schedule

	Milestone Name	Description	Projected Completion Date
A	Project Start Date	-	3/13/2017
B1	Stakeholder engagement meeting	Stakeholder engagement kick-off meeting	3/30/2017
B2	Patient eligibility data pulls	EIS Data Analyst to create a list of eligible patient population	4/30/2017
B3	Study protocol completed	Final trial protocol completed - submit a copy to PCORI	5/30/2017
B4	Patient eligibility data pulls	EIS Data Analyst to finalize list of eligible patient population and other data pulls	5/30/2017
B5	IRB Approval Obtained	Obtain IRB approval for study and submit approval letters to PCORI	7/30/2017
B6	DSMB Meeting 1	Set safety protocols and standards for data safety monitoring	7/30/2017
B7	Integration of questionnaires into patient portal	EIS Data Analyst to integrate questionnaires into MyCSLink	7/30/2017
B8	Select and register project at appropriate site for the study design (Clinicaltrials.gov, RoPR, or other as approved by PCORI before study start date)	Study Identification Number and the Primary Research Completion Date must be sent to PCORI.	7/30/2017
B9	Randomization of clinic sites	Randomization of Cedars-Sinai network offices completed; 50% to CDS arm and 50% to PEAT arm of trial	7/30/2017
B10	Passive patient recruitment begins	Passive data enrollment begins for study participants (N=960) / Study begins	8/1/2017
B11	Pharmacy data collection begins	EIS Data Analyst to begin pull data for passively enrolled patients on pharmacy data for data monitoring purposes	8/1/2017
B12	Patient baseline questionnaires	Enrolled patients begin filling out PROMIS patient reported outcome questionnaires	8/1/2017
B13	Stakeholder engagement meeting	Stakeholder engagement meeting to update on IRB submission and patient eligibility protocols and baseline data collection	8/31/2017
B14	Engagement Update	For the 6-month time intervals (i.e., 6 months, 18 months, 30 months, etc. but not at 12 months or 24 months), provide specific examples of the impact of engagement on project activities during the reporting period. Report this in the Engagement Report section of the PCORI interim progress report.	9/13/2017
B	Report Submission	Submit 6-month Interim Progress Report, Using PCORI Interim Progress Report Template	9/13/2017
C1	Study intervention begins	Study intervention begins	1/1/2018
C2	Stakeholder engagement meeting	Updates on study implementation	2/28/2018

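### Model 1 does not commit to using the baseline PROMIS Pain Interference score, and the written route for choosing covariates rests mainly on differences between the arms

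*Combined protocol and SAP*

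**What the plan says.** - **Collection.** E9 sends baseline questionnaires in the four weeks before the intervention. In Attachment C-R, milestone B12 (patient baseline questionnaires) reads "Enrolled patients begin filling out PROMIS patient reported outcome questionnaires". E4.c has PROMIS repeated monthly.
- **Primary model.** In E5.b, Model 1 is a hierarchical linear growth model whose dependent variable is the PROMIS Pain Interference T-score. Its potential covariates include "benzodiazepine use, number of office visits during intervention period, baseline HRQOL, encounter month, physician years of practice, physician gender, employment, SES". The scale meant by baseline HRQOL is not specified there.
- **Choice of covariates.** E5.a describes chi-square and t-tests for differences between the arms and continues: "using these bivariate analyses, we will identify covariates and patient- and physician-level moderators to use in the regression models". It gives no significance threshold. It then adds consultation with the Patient Partner so that suitable patient-level covariates are in the final models. E5.b says that patient- and provider-level covariates will be adjusted for, without saying which are fixed.
- **Month 0.** E5.b does not say whether the baseline score is an outcome at time 0, a covariate, or neither.
- **Power.** E5.c states "we calculated sample size using an intracluster correlation coefficient of 0.02", with "an α level of 0.05, 90% power" and "detection of a mean (SD) difference of 0.3 standard deviations on the PROMIS Pain Interference scale". It mentions no baseline adjustment and no baseline-to-follow-up correlation.

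**The concern.** The baseline value of the outcome is usually among its strongest predictors. The case for adjusting on it rests on that prognostic value and does not depend on whether the arms happen to differ. A screen on arm differences asks another question. Under randomisation such differences arise by chance, so a strongly prognostic baseline will often look balanced and give the screen no reason to pick it.

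Two things are at stake. One is precision: the interval for the arm effect may be wider than the data allow. The other is pre-specification: a chance imbalance too small to be picked up would go uncorrected, and the form of the primary estimate would depend on a choice made after seeing the data.

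**Working it through.** **Inputs from the documents.** Alpha 0.05 (two-sided assumed, since sidedness is not stated), power 90%, difference 0.3 SD and ICC 0.02 (E5.c); 320 per arm, then 960 in total (E5.c); 80 PCPs (E4.d), randomised by provider (E4.b), half to each arm (Attachment C-R, B9).

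**Assumed.** The correlation rho between baseline and follow-up Pain Interference is not given. I use 0.3 to 0.7.

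**1. The plan's own figure.** Without clustering, n per arm = 2 × ((1.960 + 1.282)/0.3)² = 233.5. The design effect is 1 + (m − 1) × 0.02 for m patients per PCP.

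- m = 640/80 = 8: 233.5 × 1.14 = 266.2, so 267 per arm.
- m = 960/80 = 12: 233.5 × 1.22 = 284.9, so 285 per arm.
- To reach 320, the design effect must be 320/233.5 = 1.370, so m is about 19.5.

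E5.c states "We calculated a sample size of 320 patients per study arm, for a total of 640 patients" but gives no cluster size. The figure is therefore not shown to be wrong, but it cannot be reproduced from 80 PCPs. The inflation does reproduce: 640 × 1.5 = 960.

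**2. Gain from adjustment, anchored at the stated 90%.** For one follow-up comparison, adjustment multiplies the variance by (1 − rho²), taken to apply equally between and within PCPs. Power = Φ(3.2415/√(1 − rho²) − 1.960).

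| rho | Power | Gain over 90% (points) |
|---|---|---|
| 0.3 | 92.5% | 2.5 |
| 0.4 | 94.3% | 4.3 |
| 0.5 | 96.3% | 6.3 |
| 0.6 | 98.2% | 8.2 |
| 0.7 | 99.5% | 9.5 |

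**3. Sensitivity to cluster size and number analysed, at rho = 0.5.**

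- 320 per arm, 8 per PCP: 94.5% unadjusted, 98.4% adjusted, a gain of 3.9 points.
- 480 per arm, 12 per PCP: 98.8% unadjusted, 99.8% adjusted, a gain of 1.0 point.

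**4. If month 0 is already an outcome (one follow-up, rho = 0.5, anchored at 90%).** With arms constrained to a common month-0 mean, power is 96.3%, so nothing is forgone. With unconstrained baseline means, the analysis is of change. Its variance factor is 2(1 − rho) = 1, so power stays at 90.0%.

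**5. If the target is an arm-by-time slope (linear trend, monthly scores, compound symmetry).** Slope variance is proportional to 1/Σ(t − t̄)². That sum is 182 for months 0 to 12 and 143 for months 1 to 12. Dropping month 0 from an unconstrained model therefore raises slope variance by 182/143 − 1 = 27%. Baseline as a main-effect covariate leaves slope variance unchanged. Keeping month 0 with a common mean lowers it by about 16% at rho = 0.5, relative to the unconstrained model with month 0.

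**6. Uncorrected imbalance (illustrative, since E5.a states no threshold).** The standard error implied by E5.c is 0.3/3.2415 = 0.093 SD. Taking the same standard error at baseline, a difference just short of 5% significance is 1.960 × 0.0925 = 0.18 SD. Left unadjusted, it moves a single follow-up comparison by rho × 0.18: 0.09 SD at rho = 0.5, or 30% of the 0.3 SD target (18% at rho 0.3, 42% at rho 0.7).

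**The case against.** The best defence is that the plan is silent here rather than wrong, and much of that stands.

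- **No drop rule is written.** A reader might infer that baseline is kept only when the arms differ, and so is omitted in about 95% of randomisations. The documents do not support this. E5.a has no threshold, does not say that balanced covariates are removed, and adds the Patient Partner route. The potential list also contains encounter month, which looks like the growth model's time variable and could hardly be subject to such a screen.
- **HRQOL covers Pain Interference.** Model 3 and the race/ethnicity entry in E6 both count this scale within HRQOL. The label therefore includes the right score, but does not single it out or make it mandatory.
- **The model is longitudinal.** The single-follow-up arithmetic is only a guide, and a growth model may already hold month 0 as an outcome. The results in steps 4 and 5 vary with how month 0 is handled, which is why the plan needs to say.
- **Baseline coverage is uncertain.** The intervention begins on 1/1/2018, while Attachment C-R has enrolment reaching 25% on 6/15/2018 and 100% on 12/31/2018. Some patients may lack a pre-intervention score, and the gains above make no deduction for that.

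None of this supplies a commitment. Consultation is discretionary, and a general promise to adjust for covariates does not name this one.

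**Conclusion.** The point holds as a gap in pre-specification. The outcome's own baseline is to be collected, but Model 1 does not commit to it. The main written route to inclusion uses the wrong criterion, and the handling of month 0 is unstated. The score may therefore be left out of the primary model.

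A reader might also infer that the trial loses about 6 points of power. It does not: the 90% in E5.c assumes no stated baseline adjustment, so nothing planned is lost. The 6.3 points are a possible gain above 90%, and they rest on an assumed rho of 0.5, a single follow-up comparison and the 90% anchor. The range is 2.5 to 9.5 points for rho 0.3 to 0.7. At rho 0.5 the gain is 3.9 points with 8 patients per PCP and 1.0 point if all 960 are analysed. The 960 includes an allowance for loss and non-response, so that last case is optimistic about numbers. For a slope target, the gain depends on how month 0 is modelled.

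The primary analysis is under-specified, not invalid. The change is worth making because it is simple and settles the choice before the data are seen.

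**What to change.** In Model 1, state that baseline PROMIS Pain Interference is always used and is exempt from the E5.a selection, whatever the observed balance.

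- **Preferred form:** keep month 0 in the outcome vector and constrain the arms to a common mean there. This also keeps patients who have follow-up scores but no baseline score.
- **If the target is an arm difference in post-baseline level:** include the baseline score as a fixed covariate. Do not restrict the outcomes to post-baseline months if the target is a slope.

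State which target applies. In Model 3, treat each outcome in the same way with its matching baseline scale.

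The cost is a sentence or two in E5.b and a cross-reference in E5.a, with no new data collection.
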